## 4.1 OVERVIEW OF STUDY DESIGN/INTERVENTION

### 4.2 Design

[figure not shown]
The study will use a single-stage phase II design. We are interested in the 2-induction BCG therapy if the overall response rate is  $\geq 80\%$  and not interested if the overall response rate is  $\leq 66\%$ . The probabilities of a type I error and type II error are set at 0.05 and 0.20, respectively.

We will enroll/continue enrolling patients until 75 patients have completed their second cystoscopy on study. On completion of the trial, if  $\geq 52$  patients had a response, the regimen will be declared effective and of interest.

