### 4.3 Intervention

**Rationale:** The current regimen of 6 intravesical instillations of BCG for high risk superficial bladder cancer is arbitrary. No randomized trials have been performed to identify the optimal number of intravesical BCG instillations needed to obtain the lowest recurrence rates.

**Treatment Plan:** Patients with high risk superficial bladder cancer will be treated with 2 induction courses (12 intravesical instillations total) of BCG. Patients will undergo a diagnostic TUR which will include a urine cytology when possible to evaluate their bladder tumor/tumors, a past TURBT and urine cytology within 60 days of treatment initiation will also suffice. If the pathological characteristics of the tumors result in the patient being deemed eligible, they will be asked to enroll in the study. A prior/current history and physical examination will also be evaluated. After the first induction course (6 intravesical instillations) of BCG, patients will be scheduled for a cystoscopy at 3 months (+/- 4 weeks). During this 3 month cystoscopy appointment patients will again submit a urine cytology prior to the procedure. If worsening tumor is found a TURBT will be scheduled at the physicians discretion. All enrolled patients will be evaluated for the primary endpoint, as defined in section 14.0, of the study, regardless of whether they received the full course of treatment.

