### **13.0 CRITERIA FOR REMOVAL FROM STUDY**

If at any time the patient develops progressive disease or experiences an unacceptable toxicity, the patient will be referred to receive standard treatment. An unacceptable toxicity is defined as severe frequency, dysuria or pain. Patients that cannot tolerate BCG instillations and refuse due to side effects are also defined as unacceptable toxicity. These patients will be evaluable for the primary endpoint of the study.

Patients with progressive disease will be considered to have experienced treatment failure, and patients with toxicities will have their outcomes ascertained 6 months after the initiation of the first BCG treatment. The number of patients, who do not complete therapy, and the reasons for not completing therapy, will be included in the final study report.

If at any time the patient is found to be ineligible for the protocol as designated in the section on Criteria for Patient/Subject Eligibility (i.e., a change in diagnosis), the patient will be removed from the study.

Patients who are removed from the study due to withdrawal of consent or who are lost to follow-up will not be considered evaluable and will be replaced.

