#### **Primary endpoint**

The study will employ a single-stage design. We are interested in the 2-induction BCG therapy if the overall response rate is  $\geq 80\%$  after the initiation of the first BCG therapy and not interested if the overall response rate is  $\leq 66\%$ . The probabilities of a type I error and type II error are set at 0.05 and 0.20, respectively. We will continue enrolling patients until 75 patients have completed their second cystoscopy on study. On completion of the trial, if  $\geq 52$  patients had a response, the regimen will be declared effective and of interest. All patients who meet the eligibility criteria for the study and enroll in it will be included in the analysis, regardless of whether they completed the full 2 BCG induction courses.

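### A patient who progresses before the 6-month cystoscopy need not count toward the 75, so one more patient is enrolled against a fixed success count

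*Combined protocol and SAP*

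**What the plan says.** Section 14.0 (Primary endpoint) gives the stopping rule: "We will continue enrolling patients until 75 patients have completed their second cystoscopy on study". Section 4.2 (Design) has the same rule in nearly the same words: "We will enroll/continue enrolling patients until 75 patients have completed their second cystoscopy on study". The second cystoscopy is the 6-month visit in Section 10.0; the first is at 3 months. In both sections success is an absolute count: if 52 or more "patients had a response, the regimen will be declared effective and of interest". Neither section ties the 52 to the number enrolled.

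Other sections define who is analysed:

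- Section 14.0: "All patients who meet the eligibility criteria for the study and enroll in it will be included in the analysis", whether or not both courses were completed.
- Section 4.3: "All enrolled patients will be evaluated for the primary endpoint", again regardless of treatment received.
- Section 13.0: a patient who progresses is referred to standard treatment and remains evaluable. "Patients with progressive disease will be considered to have experienced treatment failure".
- Section 13.0: patients who withdraw consent or are lost to follow-up "will not be considered evaluable and will be replaced". There is no exception for a patient whose progression is already on record.

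Section 12.0 assesses response at 6 months and defines progression as muscle-invasive or metastatic disease. Under Section 9.1 patients go on to the second course after the 3-month cystoscopy.

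**The concern.** The enrolment rule and the analysis rule count different people. Enrolment stops on completed 6-month cystoscopies, whereas the analysis takes in every eligible enrolled patient. A progressor who leaves for standard treatment without that cystoscopy belongs to the second group but not the first.

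The analysis sentence keeps that failure in the reported response rate. It does nothing for the decision, because a count of responders cannot fall when a failure is added to the denominator. Each such failure brings in another patient who may respond. The patients passed over in this way are not a random subset, and with no control arm nothing offsets the bias. What is at stake is the false-positive rate of the trial's only formal decision.

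**Working it through.** **1. The plan's own rule, before any top-up.** The inputs from Section 14.0 are n = 75, cutoff 52, uninteresting rate 0.66, target rate 0.80, type I error 0.05 and type II error 0.20. With X ~ Bin(75, p):

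- P(X ≥ 52 | 0.66) = 0.317 and P(X ≥ 52 | 0.80) = 0.990. The stated 0.05 is not reproduced. That is a separate error.
- The smallest cutoff at n = 75 that meets 0.05 is 57: P(X ≥ 57 | 0.66) = 0.041 and P(X ≥ 57 | 0.80) = 0.844.

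The effect of topping up is judged mainly at 57, so that the two problems stay apart. The cutoff of 57 is not in the protocol.

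**2. Following the rules for one patient.** A patient progresses at month 4 and is referred to standard treatment.

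- Section 13.0: evaluable, a treatment failure.
- Section 14.0, analysis: included as a nonresponder.
- Section 14.0, enrolment: no second cystoscopy on study, so not one of the 75, and one more patient is enrolled.
- Section 14.0, decision: the success count does not change.

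A patient with disease at 3 months who has a cystectomy before month 6 follows the same path through the enrolment rule. The difference is that no section makes this patient a failure before month 6.

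**3. Size if every such patient is a failure.** Let q be the share of enrolled patients who leave in this way without a second cystoscopy. The documents do not give q; 1%, 2% and 4% are assumptions. If the true response rate among all enrolled is 0.66, the rate among completers is 0.66/(1 − q), and the expected number of extra patients is 75q/(1 − q).

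| q (assumed) | Expected extra patients | Rate in completers | P(X ≥ 57) | P(X ≥ 52) |
|---|---|---|---|---|
| 0 | 0 | 0.660 | 0.041 | 0.317 |
| 1% | 0.8 | 0.667 | 0.053 | 0.361 |
| 2% | 1.5 | 0.673 | 0.067 | 0.409 |
| 4% | 3.1 | 0.688 | 0.108 | 0.513 |

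**4. Size if half of them would have responded to course 2.** The rate among completers becomes (0.66 − 0.5q)/(1 − q), which is 0.662, 0.663 and 0.667. P(X ≥ 57) is then 0.044, 0.047 and 0.053. This discount can apply only to patients who leave with persistent disease. Progressors are failures under Section 13.0.

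**The case against.** The strongest reply is that the protocol already deals with these patients. Progressors are evaluable failures, all eligible enrolled patients are analysed, and Section 13.0 requires the number of non-completers and their reasons in the final report. The planned path after the 3-month visit is course 2, so departures are exceptions, and no figure in the documents says how common they are. All of this stands. It protects the reported rate and makes the departures visible, but the decision count is still unprotected.

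Five stronger readings are tempting and are not supported:

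- **Everyone who misses the second cystoscopy after a bad 3-month result is a failure by definition.** This holds only for progressors. Section 12.0 assesses response at 6 months, and Section 9.1 sends patients on to the second course, which is the regimen under test.
- **A regimen could be declared a success below 66%.** With four uncounted failures, 52/79 = 65.8%. But that follows from the cutoff of 52 being too low. At 57 the same four give 57/79 = 72.2%, and it takes twelve to fall below 66% (57/87 = 65.5%).
- **The site audit fixes q.** Section 3.3 reports 13.7% non-response at 3 months. Those are patients whom this protocol keeps for course 2 and the 6-month cystoscopy, so neither that figure nor a fraction of it measures departures.
- **Progressors are replaced under Section 13.0.** The replacement sentence covers withdrawal of consent and loss to follow-up. For progressors the top-up comes from the stopping rule.
- **Later cystectomy removes a patient as ineligible.** The Section 13.0 sentence that begins "If at any time the patient is found to be ineligible for the protocol" gives a change in diagnosis as its example and does not mention treatment started after enrolment.

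**Conclusion.** The concern holds for a limited group. Followed exactly, Sections 4.2 and 14.0 top up a progressor who has no 6-month cystoscopy, while the success count stays fixed. The same happens to a patient with documented disease who leaves for non-protocol therapy before month 6. The bias from progressors is toward success. From persistent-disease leavers it is weaker, because some might have cleared on course 2.

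The size cannot be fixed from the documents. At a valid 57/75 and a true 66%, type I error goes from 0.041 to between 0.053 and 0.108 for assumed q of 1% to 4% if all are failures, and to between 0.044 and 0.053 if half would have responded. In the all-failures case even q = 1% takes an otherwise valid design just past 0.05, so correcting the threshold alone would not settle the point. The figures assume independent patients and a true rate of 66% among all enrolled.

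This is worth correcting because it lies in a stated rule and costs little to change. It is not evidence that the effect will be large.

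**What to change.** In Sections 4.2 and 14.0, replace the count of completed second cystoscopies with 75 evaluable patients. Define these as eligible enrolled patients who either:

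- have a 6-month assessment, or
- before that assessment progress, or receive cystectomy, radiation, chemotherapy or other non-protocol bladder cancer therapy for documented disease.

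The second group counts as nonresponders toward the 75 and is not topped up. In Section 13.0, add that later withdrawal or loss to follow-up does not make a patient with progression already documented non-evaluable or replaceable.

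Do not score other withdrawn or lost patients by their 3-month result. Calling them failures if they had disease at 3 months, while replacing those who were clear, would treat dropouts asymmetrically and push the rate down.

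Cost: the observed response rate may be slightly lower, a few of the 75 will have no second cystoscopy, and a patient who leaves for other therapy but might have cleared on course 2 is scored a nonresponder. No extra patients or procedures are needed; expected enrolment falls by about 1 to 3 patients over the assumed range. With all 75 counted, power at a true 80% is 0.844 for 57/75, above the planned 0.80. The change does not repair the 52/75 threshold (exact type I error 0.317), which needs its own correction.

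### The success rule of 52 or more responders in 75 patients has an exact type I error of about 32% at the 66% null, not the stated 5%

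*Combined protocol and SAP*

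**What the plan says.** The decision rule appears twice, in section 4.2 (Design) and in section 14.0 (Primary endpoint), with the same figures. The regimen is of interest if the response rate is 80% or more and not of interest if it is 66% or less. On the error rates: "The probabilities of a type I error and type II error are set at 0.05 and 0.20, respectively". On sample size: "We will continue enrolling patients until 75 patients have completed their second cystoscopy on study". On success: "if $\geq 52$ patients had a response, the regimen will be declared effective and of interest".

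Section 14.0 adds a statement on the analysis set: "All patients who meet the eligibility criteria for the study and enroll in it will be included in the analysis". Section 13.0 says that patients who withdraw consent or are lost to follow-up are not evaluable and will be replaced. No section gives a dropout allowance, another denominator or another cutoff. The documents do not say whether alpha is one-sided or two-sided.

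The 66% null matches the institution's own audit in section 3.3, where 34% of patients given BCG had failed treatment by 6 months.

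**The concern.** The cutoff looks too low on sight. At a true rate of 66%, 75 × 0.66 = 49.5 responders are expected, so 52 is only 2.5 patients above what an uninteresting regimen would give on average. A 5% test cannot sit that close to the null expectation: the standard deviation of the count is √(75 × 0.66 × 0.34) = 4.1 patients.

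This is the only decision rule for the primary endpoint. There is no control arm, so protection against a false positive rests wholly on this number. Since 66% is in effect the institution's past result, a true rate of 66% means that the second induction course has added nothing.

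**Working it through.** **Inputs** (sections 4.2 and 14.0): n = 75, cutoff r = 52, p0 = 0.66, p1 = 0.80, stated type I error 0.05, stated type II error 0.20. Alpha is taken as one-sided because the rule can succeed in one direction only.

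**Formulas.** With X the number of responders:
- type I error = P(X ≥ r), X ~ Binomial(n, 0.66)
- power = P(X ≥ r), X ~ Binomial(n, 0.80)

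**Step 1: try to reproduce the plan's figures.** For r = 52 and n = 75, type I error is 0.3167 (stated 0.05) and power is 0.9904, so type II error is 0.0096 (stated 0.20). Neither figure is reproduced. The ratio for type I error is 0.3167 / 0.05 = 6.3.

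**Step 2: try other readings.**
- More than 52, that is 53 or more: type I error 0.234.
- Normal approximation: 0.271, or 0.313 with continuity correction.
- Two-sided 0.05, that is 0.025 in the upper tail: the gap widens.

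**Step 3: find the cutoff that fits n = 75.**

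| Cutoff (of 75) | Observed rate | Type I error at 66% | Power at 80% |
|---|---|---|---|
| 52 | 69.3% | 0.317 | 0.990 |
| 53 | 70.7% | 0.234 | 0.981 |
| 54 | 72.0% | 0.165 | 0.965 |
| 55 | 73.3% | 0.110 | 0.940 |
| 56 | 74.7% | 0.069 | 0.900 |
| 57 | 76.0% | 0.041 | 0.844 |
| 58 | 77.3% | 0.023 | 0.769 |

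The smallest cutoff with type I error at or below 0.05 is 57, and it is the only one in the table that meets both stated error rates. The type I error column is also the one-sided exact p-value for that result, so outcomes of 52 to 56 responders would be called successes with p from 0.317 down to 0.069.

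**Step 4: find the n that fits a cutoff of 52.** Only n = 68 meets both error rates (type I error 0.042, power 0.812). A sample size raised from 68 to 75 (68 × 1.1 = 74.8) without updating the cutoff would explain the mismatch. That is inference; the documents do not say so.

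**Step 5: what the estimates would show.** At 52 of 75 the exact (Clopper-Pearson) 95% interval is 57.6% to 79.5%. At 57 of 75 the one-sided 95% lower bound is 66.5%, just above the null.

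**Step 6: sensitivity to the number analysed.** A fixed count becomes easier to reach as the denominator grows.

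| Patients analysed | Type I error, cutoff 52 | Type I error, cutoff 57 | Smallest valid cutoff (type I error, power) |
|---|---|---|---|
| 75 | 0.317 | 0.041 | 57 (0.041, 0.844) |
| 76 | 0.377 | 0.060 | 58 (0.035, 0.829) |
| 77 | 0.440 | 0.084 | 59 (0.030, 0.813) |
| 78 | 0.503 | 0.114 | 59 (0.044, 0.864) |

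**The case against.** The arithmetic is not open to dispute. The best defence of the rule itself is that 75 might include an allowance for dropout, with about 68 patients evaluable. The text rules this out: the 75 are patients who have completed the second cystoscopy, and withdrawn or lost patients are replaced, so attrition does not shrink the denominator.

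Other objections bear on the size of the claim and on the remedy.

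- *The 32% applies at a true rate of exactly 66%.* This is so, and that is where type I error is defined. For worse regimens the chance of a false success is lower: 20.1% at 64%, 11.6% at 62%, 6.1% at 60%.
- *Not every positive result would mislead.* Also correct. With 57 or more responders of 75 the claim holds at the one-sided 5% level; the harm lies in the band from 52 to 56.
- *Sidedness is assumed.* One-sided is the natural reading. If 0.025 in the upper tail was meant, the cutoff is 58, with type I error 0.023 and power 0.769. That misses the stated 0.80, and more patients would be needed (82 patients with 63 or more responders gives 0.023 and 0.806).
- *It is not known whether 52 or 75 is the mistaken number.* True, but 52 of 68 would contradict the 75 stated in both sections, whereas 57 of 75 leaves the sample size alone.
- *Changing one number may not be enough.* This point stands. The 75 is a stopping rule for enrolment, while the analysis takes in all eligible enrolled patients. A patient who progresses before the second cystoscopy counts as a failure but may not count toward the 75, and patients already enrolled when the 75th completes may add to the total. One extra patient takes a fixed cutoff of 57 to a type I error of 0.060.

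**Conclusion.** The concern holds. The rule as written has an exact type I error of 0.317 against the stated 0.05, and a type II error of 0.010 against the stated 0.20. The result rests only on the plan's own figures, on the binomial model, and on 75 patients being analysed; more than 75 makes it worse. It does not depend on sidedness, since 0.317 exceeds either limit. The replacement cutoff of 57 does depend on two assumptions: one-sided alpha of 0.05 and exactly 75 patients analysed. The rule must be corrected before it is used to declare the regimen effective.

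**What to change.** In sections 4.2 and 14.0, replace the success rule with 57 or more responders of 75 patients analysed. Beside it, state that alpha is one-sided and that the exact type I error is 0.041 and the exact power 0.844. Report the response rate with its exact confidence interval.

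In the same amendment, define the primary denominator: say whether patients who progress before the second cystoscopy, and those still on study when the 75th completes it, are counted. Add that if the number analysed is not 75, the cutoff is the smallest count with exact type I error at or below 0.05 at 66% (for example 58 of 76 or 59 of 78).

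The cost is protocol wording: one number in two places, plus a sentence or two on sidedness and the denominator. No extra patients are needed under one-sided alpha. The bar for success rises from 69.3% to 76.0%, and power falls from 0.990 to 0.844, still above the planned 0.80.

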#### **Secondary endpoints**

We will also assess the proportion of patients whose disease progresses at 6 months. The 6 month progression rate will be presented along with a 95% confidence interval based on the binomial distribution.

## **Accrual**

We estimate 3-5 patients per month will be accrued to this protocol.

### **15.1 RESEARCH PARTICIPANT REGISTRATION AND RANDOMIZATION PROCEDURES**

#### **15.2 Research Participant Registration**

Confirm eligibility as defined in the section entitled Inclusion/Exclusion Criteria. Obtain informed consent, by following procedures defined in section entitled Informed Consent Procedures. During the registration process registering individuals will be required to complete a protocol specific Eligibility Checklist.

The individual signing the Eligibility Checklist is confirming that the participant is eligible to enroll in the study. Study staff are responsible for ensuring that all institutional requirements necessary to enroll a participant to the study have been completed. See related Clinical Research Policy and Procedure #401 (Protocol Participant Registration).

### **16.1 DATA MANAGEMENT ISSUES**

A research study assistant (RSA) will be assigned to the study. The responsibilities of the RSA include project compliance, data collection, abstraction and entry, data reporting, regulatory monitoring, problem resolution and prioritization, and coordination of the activities of the protocol study team. The data collected for this study will be entered into Caisis, a secure departmental database. A minimal data set will be added to CRDB. Source documentation will be available to support the computerized patient record.

#### **16.2 Quality Assurance**

Monthly registration reports will be generated to monitor patient accruals and completeness of registration data. Routine data quality reports will be generated to assess missing data and inconsistencies. Accrual rates and extent and accuracy of evaluations and follow-up will be monitored periodically throughout the study period, and potential problems will be brought to the attention of the study team for discussion and action. Random-sample data quality and protocol compliance audits will be conducted by the study team at a minimum of once every 6 months, and more frequently if indicated.

#### **16.3 Data and Safety Monitoring**

The Data and Safety Monitoring (DSM) Plans at Memorial Sloan-Kettering Cancer Center were approved by the National Cancer Institute in September 2001. The plans address the new policies set forth by the NCI in the document entitled "Policy of the National Cancer Institute for Data and Safety Monitoring of Clinical Trials" which

can be found at: <http://cancertrials.nci.nih.gov/researchers/dsm/index.html>. The DSM Plans at MSKCC were established and are monitored by the Clinical Research Administration. The MSKCC Data and Safety Monitoring Plans can be found on the MSKCC Intranet at: <http://mskweb2.mskcc.org/irb/index.htm>

There are several different mechanisms by which clinical trials are monitored for data, safety and quality. There are institutional processes in place for quality assurance (e.g., protocol monitoring, compliance and data verification audits, therapeutic response, and staff education on clinical research QA) and departmental procedures for quality control, plus there are two institutional committees that are responsible for monitoring the activities of our clinical trials programs. The committees: *Data and Safety Monitoring Committee (DSMC)* for Phase I and II clinical trials, and the *Data and Safety Monitoring Board (DSMB)* for Phase III clinical trials, report to the Center's Research Council and Institutional Review Board.

During the protocol development and review process, each protocol will be assessed for its level of risk and degree of monitoring required. Every type of protocol (e.g., NIH sponsored, in-house sponsored, industrial sponsored, NCI cooperative group, etc.) will be addressed and the monitoring procedures will be established at the time of protocol activation.

